COLUMBIA UNIVERSITY
MEDICAL CENTER

**A Feasibility Study Examining the Use of Non-Invasive Focused Ultrasound (FUS)
with oral Panobinostat Administration in Children with Progressive Diffuse
Midline Glioma (DMG)**

Short Title: FUS Panobinostat for DMG
Columbia University Irving Medical Center

KEY TRIALS CONTACTS:

PRINCIPAL INVESTIGATOR:

[name]., Ph.D.

[name]
[name]
T: [contact]
[name]
[contact]

CO-INVESTIGATORS:

[name].

[name]
T: [contact]
[contact]

[name].

[name]
[name]
[name]
T: [contact]
[contact]

[name]., Ph.D.

[name]
[name]
T: [contact]
[contact]

[name].

[name]
[name]
T: [contact]
[contact]

[name]., Ph.D.

[name]
[name]
T: [contact]
[contact]

[name].

[name]
[name]
T: [contact]
[contact]

[figure not shown]
STATISTICIAN:

[name].

[name]
[name]
T: [name]
[contact]

| | | |
|-----------------------------------------------------------|--------------------------------------------------------------------------------------------------------------------------------------------------------------------------------------|--------------------------------------------------------------------------|
| Trial Title | Feasibility Study Examining the use of Non-Invasive Focused Ultrasound (FUS) with oral Panobinostat Administration in Children with progressive Diffuse Midline Glioma (DMG). | |
| Short Title | FUS Panobinostat for DMG | |
| Trial Design | Prospective non-randomized single arm feasibility study | |
| Trial Participants | Children | |
| Planned Sample Size | Maximum 15 subjects | |
| Treatment duration | 6 months | |
| Follow-up duration | 2 years | |
| Investigational Medical Device: Focused Ultrasound | | |
| | Objectives | Outcome measures |
| Primary Endpoint | To evaluate the safety and feasibility of using FUS to open one, two or three tumor sites for administration of Panobinostat in children with progressive DMG | Physical exam, laboratory studies, |
| Secondary Endpoints | To determine blood brain barrier/tumor imaging changes using FUS in children with progressive DMG | Documenting changes in the pattern of contrast enhancement on MRI |

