6. STUDY OBJECTIVES

6.1 Primary Objective

The primary objective of this study is to evaluate the feasibility of safely opening the BBB in children with progressive DMG treated with oral Panobinostat using FUS with DEFINITY® microbubbles and neuro-navigator-controlled sonication.

With the current study we are planning to evaluate the safety and feasibility of using FUS and open-space neuronavigator-controlled sonication to open one, two or three tumor sites. For the purpose of the study we will be administering oral Panobinostat in children with progressive DMG. This drug has a known toxicity profile, dose and well documented efficacy against many metastatic cancers. Successful opening and closing of the BBB will be confirmed with periodic MRIs.

Safety will be assessed by evaluation of physical and neurologic examinations, laboratory studies, radiographic studies, and by adverse events as per the CTCAE version 5.0. An adverse event is

any new or worsening symptom or clinical finding which occurs during the study period. Adverse events are to be recorded irrespective of causality on the adverse event form. Each event will be described by its severity (mild, moderate, severe, life-threatening), duration, and relation to the study medication (unrelated, unlikely, possible, probable, and definite).

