10.1 Sample Size Determination

A minimum of 3 and maximum of 15 patients will be recruited in the study. The minimum number of subjects is to account for “dose” limiting toxicities disallowing more subjects to be enrolled. As this is a feasibility study, the power and sample size is not justified. However, successful methodology will be concluded if the BBB opening is safely opened in at least 75% of the cases as evidenced on MRI. The scan with the BBB opening will be compared to the scan before BBB opening for each patient. Power analysis shows that for a detectable difference of 72 mm^3 (after BBB opening - before BBB opening) and a standard deviation of 50 mm^3 , at least 6 subjects are needed to report a result at the level of $\alpha=0.05$ and Power=0.80 with paired student's t-test.

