10.2 Statistical Data Analysis

The data analysis will be descriptive. The continuous scan measures will be summarized by median, minimum and maximum. The categorical measures will be summarized by frequency and proportions, such as adverse events. Nonparametric Wilcoxon signed-rank test will be used to compare the gadolinium enhancement in the patient's brain before and after BBB opening.

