12.4 Early Withdrawal of Subjects

- If the subject fails to comply with the defined treatment plan and follow-up evaluations, the subject may be removed from the study at the discretion of the treatment investigator
- If the subject withdraws consent for continued participation, he/she will be removed from the study
- If the subject develops significant, new neurologic deficits or a change in level of consciousness a CT or MR scan may be performed to evaluate for hemorrhage/edema. If symptoms remain unmanageable by medications, craniotomy may be performed for resection of tumor, necrosis, or hemorrhage if medically indicated
- The reason for study removal and the date the subject was removed should be documented in the Case Report Form (CRF)
- If the treatment related toxicity experienced toxicity (Grade 2 or higher) persists for more than 21 days or ≥1 Dose Limiting Toxicity, the subject will not have the subsequent FUS and early withdrawal will be considered.

The primary endpoint of this study is safety. As such, subjects will be withdrawn from the study as per the guidelines outlined above. Should similar toxicities occur in more than one subject; early interruption of the study will be considered.

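### The power statement in 10.1 belongs to a paired t-test that neither tests the 75% success rule nor matches the signed-rank test named in 10.2

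*Combined protocol and SAP*

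**What the plan says.** Section 10.1 sets a range of 3 to 15 subjects and says that power and sample size are not justified because this is a feasibility study. It then gives the success criterion: "successful methodology will be concluded if the BBB opening is safely opened in at least 75% of the cases as evidenced on MRI". Next comes a power calculation for the before/after difference in enhancement volume (difference 72 mm³, SD 50 mm³), which concludes that "at least 6 subjects are needed to report a result at the level of" alpha 0.05 with power 0.80, using a paired t-test.

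Section 10.2 calls the analysis descriptive and names a different test: "Nonparametric Wilcoxon signed-rank test will be used to compare the gadolinium enhancement in the patient's brain before and after BBB opening". It gives no alpha and no sidedness, and it does not mention the 75% proportion or an interval for it.

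The primary endpoint is worded in three ways:

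- Synopsis: "To evaluate the safety and feasibility of using FUS to open one, two or three tumor sites", with "Physical exam, laboratory studies" as the visible outcome measures. Under the secondary endpoints it lists "Documenting changes in the pattern of contrast enhancement on MRI".
- Section 6.1: "The primary objective of this study is to evaluate the feasibility of safely opening the BBB in children with progressive DMG". The same section says that opening and closing are confirmed by MRI.
- Section 12.4: "The primary endpoint of this study is safety".

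**The concern.** The criterion that decides feasibility is a proportion. The sample-size paragraph attaches its only alpha and power to a mean. A before/after test asks whether enhancement rises at all. It does not ask whether the barrier opens in three quarters of children, so the 80% power figure tells the reader nothing about how well the trial can answer its own success question. The figure also does not carry over to the test that section 10.2 will run.

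The plan does not say how the test and the rule relate. A small p-value could therefore appear in the report beside a failed 75% rule, or a passed rule beside a non-significant test, with nothing in the plan to guide the reader. Section 12.4 adds to this: read alone, it leaves out the feasibility component that the 75% rule is meant to judge.

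**Working it through.** **Inputs.** From 10.1: difference 72 mm³, SD 50 mm³ (read as the SD of the paired differences), alpha 0.05, power 0.80, n=6, N from 3 to 15, threshold 75%. From 10.2: signed-rank test. Assumed, because the plan does not say: the subject is the unit, testing is two-sided, unopened subjects have zero change and are dropped from the ranking, and opened subjects have a positive change.

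**1. The plan's own figure.** Standardised difference = 72/50 = 1.44. Power of the two-sided paired t-test comes from the noncentral t with n−1 degrees of freedom and noncentrality 1.44√n.

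- n=5: power 0.677.
- n=6: noncentrality 1.44 × √6 = 3.53, power 0.803.

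So n=6 reproduces. A one-sided test would need only n=5 (0.837), so the plan's figure implies two-sided testing.

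**2. The same inputs with the test in 10.2.** At n=6 the exact two-sided signed-rank test reaches p<0.05 only when all six differences have the same sign: p = 2/2⁶ = 0.031. The next possible value is 4/2⁶ = 0.0625. Under normal differences:

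- P(one difference positive) = Φ(1.44) = 0.925.
- Power at n=6 = 0.925⁶ ≈ 0.63 (the all-negative term is negligible). Simulation with 40,000 runs gives 0.627.
- Power at n=7 is about 0.85 by simulation, the first size above 0.80.

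**3. Test against rule.** With k openers, all changes positive and zeros dropped, p = 2/2ᵏ, so any k of 6 or more is significant. The rule needs at least 0.75N openers: 12 at N=15 (0.75 × 15 = 11.25) and 5 at N=6 (0.75 × 6 = 4.5).

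| N=15, true opening rate | P(p<0.05) = P(X≥6) | P(rule met) = P(X≥12) | P(significant, rule failed) = P(6≤X≤11) |
|---|---|---|---|
| 50% | 0.849 | 0.018 | 0.83 |
| 60% | 0.966 | 0.091 | 0.88 |

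In the other direction, at N=6 with 5 opened the rule is met (83%), but p = 2/2⁵ = 0.0625. The result is also 0.0625 if the sixth change is negative and the smallest in size. If the sixth change is positive, p = 0.031 and the two agree.

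**4. What the deciding proportion can show.** Exact (Clopper-Pearson) 95% limits are the 0.025 quantile of Beta(k, n−k+1) and the 0.975 quantile of Beta(k+1, n−k).

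- 5/6 = 0.83: 0.36 to 1.00.
- 12/15 = 0.80: 0.52 to 0.96.

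Each count is the smallest that passes at its sample size, and in both cases the lower limit lies well below 0.75.

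**The case against.** The strongest reply is that the plan does have one deciding criterion. Only the 75% rule is tied to a conclusion. No section attaches success to a p-value, and 10.2 calls the analysis descriptive. This stands. A reader might infer that several contrasts compete for the verdict, and the documents do not support that. Nor do they support the inference that the verdict rests on a secondary measure: 6.1 places MRI-confirmed safe opening under the primary objective, and the synopsis item is the pattern of enhancement, which overlaps with the binary opening definition in 7.6.1 but is not the same. The synopsis cell listing physical exam and laboratory studies ends on a comma and may be cut off, so the absence of MRI there proves nothing.

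Two further inferences also fail. Section 7.5 schedules an opening scan in each of six cycles, so one might suspect six tests and an inflated error rate. But 10.1 compares one scan with the scan before opening and 10.2 names one test, so repeated testing would be an assumed practice. One might also object that 3 to 5 subjects can never reach p<0.05 on the signed-rank test, but 10.1 already says that at least 6 are needed to report such a result.

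It is fair, too, that a test and a rule answering different questions may differ without contradiction. If half the children open, enhancement did rise. That does not rescue the power statement, which is offered as the sample-size support in the paragraph that sets the rule and does not apply to that rule or to the planned test.

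**Conclusion.** The point holds in a limited form. The 75% rule is the single success criterion, but the plan gives no precision or power for it. The stated 0.80 at n=6 is correct for a two-sided paired t-test and is about 0.63 for the signed-rank test that will be used. The test and the rule can disagree in either direction. The largest gap shown is at N=15 with a 50% opening rate: 0.85 for significance against 0.018 for the rule.

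The power comparison rests on normal differences and two-sided testing. The disagreement figures also rest on the subject as unit (10.1 does not define its cases) and zero change in unopened subjects. The N=6 example depends on the sidedness: one-sided, 5 of 6 opened with the sixth change zero gives p = 0.031. The mismatch between the rule and the powered quantity needs none of these assumptions.

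The endpoint wording is a smaller matter. Section 12.4 is narrower than the synopsis and 6.1, and the three should agree. This is not evidence that safety lacks rules, because 7.2, 12.2 and 12.3 cover it. The change is worth making but does not call the design into question.

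**What to change.** 1. In 10.1, replace the paired t-test power statement with the exact 95% confidence interval of the opening proportion at the planned sizes, for example 5/6 (0.36 to 1.00) and 12/15 (0.52 to 0.96). At minimum, restate the power for the signed-rank test (about 0.63 at n=6, about 0.85 at n=7).
2. In 10.2, report the proportion opened, with the subject as the unit and its exact confidence interval, as the feasibility result. Label the signed-rank comparison exploratory, name its scans (Cycle 1 Day 1 against screening), and state that no success claim rests on it.
3. Reconcile the primary-endpoint wording in 12.4 and the synopsis with 6.1 and 10.1.

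The cost is wording only: no new data, visits or scans. The trial gives up the 80% power claim, and the precision then shown for the deciding outcome is modest.

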7.2 Trial Design

The trial will follow a 3+3 “NOTS” or Number of Tumor Sites escalation scheme. The “number of tumor sites” in reference to here in the number of openings in the blood brain barrier using Focused Ultrasound (FUS). Subjects will start the first cycle of the treatment arm with 1 tumor site and move on to incrementing NOTS levels as depicted in Figure 3, if no dose limiting toxicities

(DLTs) are observed (we use the term Dose Limiting Toxicity where dose = Number of Tumor Sites (NOTS)):

- 1 tumor site (level "NOTS Level A"),
- 2 tumor sites (level "NOTS Level B") or
- 3 tumor sites (level "NOTS Level C")

For a detailed description of DLTs please refer to [Section 12.2](#).

[figure not shown]

Figure 3: NOTS (Number of tumor Sites) Escalation Schema

For each subject the following FUS NOTS escalation scheme will be followed:

- Each subject will start off with receiving FUS treatment in 1 tumor site (NOTS Level A) for Cycles 1 and 2.
- If 0 DLTs are noted during pre-cycle 3 follow-ups and MRI (without contrast), the subject will receive FUS treatment at 2 tumor sites (NOTS Level B) in the 3rd cycle.
 - If 1 DLT is noted during pre-cycle 3 follow-ups and MRI (without contrast), the subject will discontinue treatments and will come off the study (please refer to [Section 12.3](#) for Early Stopping Guidelines). Other subjects may continue to enroll.
 - If 2 DLTs are noted at the same NOTS level, enrollment will be halted following Early Stopping Guidelines detailed in [Section 12.3](#).
- If 0 DLTs are noted during pre-cycle 4 MRI (without contrast) and follow-up, the subject will continue to receive FUS treatment at 2 tumor sites (NOTS Level B) in the 4th cycle.
 - If 1 DLT is noted during pre-cycle 4 follow-ups and MRI (without contrast), the subject will discontinue treatments and will come off the study (please refer to [Section 12.3](#) for Early Stopping Guidelines).

refer to [section 12.3](#) for Early Stopping Guidelines). Other subjects may continue to enroll.

- If 2 DLTs are noted at the same NOTS level, enrollment will be halted following Early Stopping Guidelines detailed in [Section 12.3](#).
- If 0 DLTs are noted during pre-cycle 5 MRI (without contrast) and follow-up, the subject will receive the next escalated FUS treatment at 3 tumor sites (NOTS Level C) in the 5th cycle.

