During the mid-cycle at different time-points (as described in section [7.4](#) and [7.5](#) below), MRIs with gadolinium contrast will be conducted to ensure proper opening and closure of the BBB. If the subject's MRI shows any anomaly, the subject will be removed from the study and will continue on regular drug treatment as decided by the study team. The subject will follow the schema below.

7.4 Schematic Overview of Panobinostat Treatment for Week 1** Cycle 1

**Week 2 of each cycle will follow a similar schema with the exception of MRIs with contrast conducted to evaluate opening and closing of the BBB.

**Cycles 2 and 4 will follow a similar schema with the exception of an MRI to confirm closure of the BBB on Day 3.

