7.5 Treatment MRIs

Treatment MRI breakdown:

- 1 cycle of Panobinostat= 2 weeks of 3 alternate treatment days. Subjects will undergo 6 cycles, each spaced 1 week apart.
- In each cycle, subjects will receive Focused Ultrasound (NgFUS) and injection of DEFINITY® microbubbles using NgFUS system in the Radiation Oncology Suite on Days 1, 3, and 5 (all treatment days).
- **MRI to Determine Opening of Blood Brain Barrier:** On Week 1 Day 1 of each cycle, 2-4 hours post FUS treatment with DEFINITY® microbubbles on Day 1, subjects will receive an MRI with injection of Gadolinium contrast.
- Treatment includes receiving Oral Panobinostat at 15 mg/m² on the days of NgFUS treatment.
- **MRI to Confirm Closure of Blood Brain Barrier:** On Week 1 Day 3 of every other cycle (Cycles 1, 3 and 5), subjects will undergo MRI with gadolinium pre Day 3 FUS treatment to ensure closure of the blood brain barrier. This MRI will be conducted within 24-48 hours of the completion of the Day 1 FUS treatment.
- A number of tumor sites (NOTS) escalation scheme for the number of tumor sites targeted by FUS will be followed as laid out in [section 7.2](#). As stated in the section, an MRI (without contrast) will be performed prior to each escalation to clear the subject of any possible DLTs and increase in tumor size.

Subjects will receive FUS treatment in the Radiation Oncology Suite and drug treatments in either the Outpatient Clinic on HIP-7 or in Radiation Oncology immediately after the FUS treatment. Subjects will be monitored by the study team with Neurological Exams on treatment days, as determined necessary. Subjects will not be kept as inpatients for treatment days and will be discharged following completion of treatment day, unless deemed necessary by the study team.

See [Appendix A](#) and [B](#) on pages 47 and 49 respectively for a detailed breakdown of visits and data collected.

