7.6 Opening and Closing of the BBB

7.6.1 Radiological Evidence of the BBB Opening

The BBB will be determined to be open if within 5mm of site of FUS, there is evidence of enhancement seen on T1 weighted post contrast images.

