12.3 Early Stopping Guidelines

In the event 2 DLTs occur for more than 1 subject at a NOTS (number of tumor sites) level (as defined in [section 7.2](#)), study enrollment will be immediately halted. There will be at least 14 days following completion of the FUS treatment of the patient(s) on study before any subsequent patient is enrolled. After re-evaluation and consultation with the HICCC DSMC board, the trial may re-initiate enrollment with adjusted treatment parameters after a consensus is agreed upon by the Sponsor-Investigator and the HICCC DSMC, and a subsequent modification is reviewed/approved by the local PRMC/IRB. If a consensus cannot be reached, no further enrollment will be permitted on the trial and closure procedures will be initiated. In addition, the study will be discontinued at any given time if more than 20% of patients experiencing medical complications including the development of significant, irreversible deterioration during the treatment. With this rule and under the assumption of the true probability of having the medical complication is 10%, the probability of stopping the study due to the medical complication is 0.02 when the targeted total sample size is 6 and is 0.053 when the targeted total sample size is 9.

If the MRI to confirm opening of the BBB for any subject is irregular at any time during the cycles, the subject will not receive the scheduled dose treatment until a decision is made by the investigating team.

If the MRI confirm the closure of the BBB for any subject are irregular at any time, the subject will not receive any further FUS treatments and will receive another MRI to confirm closure every 48 hours for a maximum of 3 times. If the subject does not show BBB closure after 3 MRIs, the subject will come off the study. The subject will be able to receive the scheduled dose of drug, unless otherwise specified by the investigating team.

Response and progression will be evaluated in this study using the international criteria proposed by the updated Pediatric Response Assessment in Neuro-oncology (RANO) guidelines[49].

| Criterion | Complete Response | Partial Response | Stable Disease | Progressive Disease |
|----------------------------------------|---------------------|---------------------|---------------------------------|---------------------|
| T1-weighted post-Gd measurable disease | None | ≥50% decrease | <50% decrease but <25% increase | ≥25% increase |

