12.6 Stopping Rules

Redundant safety features have been added to the hardware of the device, as grounding for the transducer, safety switch for the amplifier and function generator. Additionally, we will incorporate safety valves in our software. For any signs showing safety risk including high cavitation dose in the acoustic monitoring or unstable vital signs, the device can be stopped from the computer user interface and/or an emergency stop button. Treatment will be stopped in the case of any reaction of the subject to the ultrasound exposure or microbubble infusion. Pulse oximetry will be used during MRI scans to mitigate the risk of anaphylactic reaction to MRI contrast agents.

The investigation will be terminated in case of any death, life threatening event, or any other serious adverse event (including disability or clinically significant manifestation of local hemorrhage or edema) due to the procedure. An episode of status epilepticus during treatment will terminate the session immediately.

If the selected ultrasound settings (i.e., MI of 0.4) do not successfully open the BBB in 3 subjects, FDA will be contacted via a submission of an IND supplement, to discuss revising the protocol's focused ultrasound parameters.

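### The single 75% opening criterion is not tied to site or NOTS level, so on several permitted readings it is met even if the third site never opens

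*Combined protocol and SAP*

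**What the plan says.** Section 6.1 sets out to evaluate the safety and feasibility of FUS and neuronavigated "sonication to open one, two or three tumor sites".

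Section 7.2 gives each child one site in cycles 1 and 2 (Level A), two in cycles 3 and 4 (Level B) and three in cycles 5 and 6 (Level C). The step up depends on DLTs, checked with a non-contrast MRI: "If 0 DLTs are noted during pre-cycle 5 MRI (without contrast) and follow-up, the subject will receive the next escalated FUS treatment", here at three sites.

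Opening is imaged once per cycle, with gadolinium: "On Week 1 Day 1 of each cycle, 2-4 hours post FUS treatment" (Section 7.5). Section 7.6.1 calls the barrier open if "within 5mm of site of FUS, there is evidence of enhancement seen on T1 weighted post contrast images". It does not say how many of two or three targeted sites must meet this.

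The success criterion is in Section 10.1: "successful methodology will be concluded if the BBB opening is safely opened in at least 75% of the cases as evidenced on MRI". Section 10.2 makes the analysis descriptive and has no analysis by level.

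Three other provisions touch on failed opening:
- Section 7.3: if the "MRI shows any anomaly, the subject will be removed from the study".
- Section 12.3: "If the MRI to confirm opening of the BBB for any subject is irregular at any time during the cycles", the dose is withheld until the team decides.
- Section 12.6: FDA is contacted if the settings "do not successfully open the BBB in 3 subjects".

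**The concern.** The number of sites is the one thing this trial escalates, so the useful feasibility result is up to how many sites the barrier can be opened. A criterion pooled over levels does not answer that. Every completer contributes more first-site and second-site results than third-site results, and every early leaver adds further to the lower levels. Good results at Levels A and B can therefore carry the 75%.

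Because a case is undefined, the denominator could also be chosen after the scans are seen, and different choices give opposite verdicts on the same scans. At stake is a report that the method succeeds for up to three sites when the third has not opened, and a later study planned on that basis.

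**Working it through.** **Inputs.** Sites per cycle 1, 1, 2, 2, 3, 3 (Section 7.2). One opening MRI per cycle, on Week 1 Day 1 (7.5). Opening judged around the sonicated site (7.6.1). Threshold 75% (10.1). Assumptions: the scan covers every site sonicated that day; the third site is the one added at Level C; a session is a Week 1 Day 1 session with its MRI. The opening rates and stopping patterns below are also assumed.

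**The plan's own figure.** Section 10.1 states 6 subjects for a paired t-test. With effect 72/50 = 1.44 and two-sided alpha 0.05, exact power is 0.677 at n = 5 and 0.803 at n = 6, so the figure reproduces. It concerns a difference in volume. The plan gives no operating figure for the 75% rule.

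**Step 1: counts for a completer.** First sites 6, second sites 4, third sites 2: 12 site-scans in 6 sessions.

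**Step 2: third site never opens, the others always do.**

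| Meaning of a case | Result | Against 75% |
|---|---|---|
| One site on one scan | (6 + 4 + 0)/12 = 83% | met |
| Session, any site open | 6/6 = 100% | met |
| Subject, any opening | 100% | met |
| Session, all targeted sites open | 4/6 = 67% | missed |
| Subject, all sites open at every level reached | 0% of those reaching Level C | missed |

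**Step 3: early stopping.** Let f be the fraction of children finishing Level B who complete both Level C cycles.
- If the rest stop after cycle 4, the all-sites session rate is 4/(4 + 2f). This is at least 0.75 when f ≤ 2/3, so the strict session reading is met again.
- If the rest stop after cycle 5, it is 4/(5 + f), which needs f ≤ 1/3.
- A child removed after a closed third site in cycle 5 contributes 8/9 = 89% of site-scans, against 10/12 = 83% for a completer. Removal raises the pooled figure.

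**Step 4: chance of passing on pooled site-scans.** Six completers give 72 site-scans, so 0.75 × 72 = 54 must be open. With the third site never open, these must come from 6 × 10 = 60 first-site and second-site scans.
- Independent scans: P(Bin(60, 0.95) ≥ 54) = 0.97; P(Bin(60, 0.90) ≥ 54) = 0.61.
- Full agreement within a child: five children give only 50, so all six must open. 0.95^6 = 0.74; 0.90^6 = 0.53.

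**Step 5: the same case by level.** Level A 2/2, Level B 4/4, Level C 4/6 = 67%, third site 0/2. Only Level C fails. A level-wide 75% alone is not enough: if the third site opened on half its scans and the others always did, Level C would score (2 + 2 + 1)/6 = 83%. The added site needs its own condition.

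**The case against.** The strongest reply is that this is a safety study. Section 12.4 names safety as the primary endpoint, the synopsis lists imaging changes as secondary, Section 10.1 disclaims a sample size justification, and Section 10.2 is descriptive. Escalating on DLTs alone suits that design, and Section 10.1 speaks of a successful methodology, not of three-site feasibility. The point about escalation stands. The rest does not remove the gap: Section 6.1 makes feasible opening the primary objective, and Section 10.1 fixes a threshold for declaring success.

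Several stronger readings are tempting, and the documents do not support them.
- *A third site that never opens passes however a case is read.* It does not. Both strict readings fail for completers. Section 10.1 goes on to compare scans for each patient and Section 12.6 counts subjects, so a subject-level meaning is plausible.
- *A child moves to three sites whatever the second site did.* A contrast opening MRI is taken in both Level B cycles, and 7.3 or 12.3 may act on a failed opening. Their terms are undefined, however, they act on one child, and they do not enter the 75% count. Section 12.6 does not say whether failure of an added site counts.
- *No added site need open at all.* In completers that holds only where any open site or any opening suffices; pooled site-scans give 6/12 = 50%, a failure.
- *The third site is likely to fail.* Table I gives the same settings for each location, and nothing in the documents predicts 0% beside 95%. The case is a stress test of the rule.

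The per-session or per-site wording of the microbubble dose in Table I is a separate clarification and no part of this point.

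**Conclusion.** The concern holds in this form: the 75% criterion has no defined case and is pooled over levels, so it can declare success without showing that the site added at Level C opens. With that site never open and the others always open, three readings pass (83%, 100%, 100%) and two fail for completers (67%, 0%). The strict session reading passes again if at most two-thirds of those finishing Level B complete both Level C cycles and the rest stop after cycle 4.

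These proportions follow from Sections 7.2 and 7.5, apart from the stopping pattern, which is assumed. The chance of passing on pooled site-scans with six completers is 0.97 or 0.74 at 95% opening of the first two sites, and 0.61 or 0.53 at 90%. The first of each pair assumes independent scans, the second full agreement within a child. A reader might infer that the plan will overstate three-site feasibility. The documents support only that it can, because they leave the choice of reading open.

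**What to change.** In Section 10.1:
- Define a case as one targeted site on a Week 1 Day 1 opening MRI, judged by 7.6.1.
- Apply the 75% separately at each NOTS level, and require the site added at that level to reach 75% as well. Claim feasibility only for levels that meet both.
- Keep scans already taken in the count if a child is later removed.
- Make no feasibility claim for a level reached by fewer children than a stated minimum, for example 3, the protocol's minimum enrolment. Without one, a single child could decide Level C: at 50% true third-site opening, with that child's two scans agreeing, the third-site condition passes with probability 0.50.
- Report, by level, sites open and sessions with all targeted sites open, with numbers of children and scans. Give exact intervals as descriptive only, because scans cluster within child.

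Record site order on the CRF. No extra scans are needed, and treatment and stopping rules are unchanged.

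The cost is small numbers per level: 8 of 10 has an exact 95% interval of 44% to 97%, so a level that truly works may miss 75%. Taken alone, the third-site condition at 90% true opening passes with probability 0.93 on 10 scans (8 needed) and 0.97 on 12 (9 needed) if scans are independent, or 0.92 and 0.89 for 5 and 6 children whose two scans agree. At 50% true opening the corresponding figures are 0.05 and 0.07, or 0.19 and 0.11.
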